## **11. STUDY TREATMENT USE**

### **11.1. Regimen**

Refer to and follow the DHA for specific instructions on the handling, preparation, administration, and disposal of the study treatment.

Please see Section 4.2 (Schedule of Events) for the study treatment infusion schedule during the placebo-controlled and LTE periods of the study.

Aducanumab is to be administered by IV infusion following dilution into saline. See Section 12 for details of aducanumab study treatment.

#### **11.1.1. Aducanumab**

The Sponsor will provide aducanumab to study sites.

#### **11.1.2. Placebo**

Placebo (0.9% sodium chloride) will be supplied by the study site.

### **11.2. Modification of Dose and/or Treatment Schedule**

Refer to Section 7.2.1 (dose suspension) and Section 7.2.2 (infusion interruption). Doses should be administered at least 21 days apart. If the dosing interval cannot be met, the dose administration should be assessed by the study medical monitor.

### **11.3. Precautions**

Not applicable.

### **11.4. Compliance**

Compliance with treatment dosing is to be monitored and recorded by unblinded site staff.

### **11.5. Prior and Concomitant Therapy and Procedures**

#### **11.5.1. Prior and Concomitant Therapy**

Prior AD medication use within the 12 months prior to Screening will be captured.

A concomitant therapy is any drug or substance administered between the informed consent and until the subject's final clinic visit (including the FU Visit).

No premedication (e.g., anti-allergy drugs, antipyretic analgesics) should be used prior to the start of study treatment infusion unless discussed with the study medical monitor in advance.

CONFIDENTIAL

The information contained herein may not be used, disclosed, or published without the written consent of Biogen MA Inc.

#### 11.5.1.1. Allowed Concomitant Therapy

- Medications for chronic conditions are allowed at a stable dose during the study as long as the subject has been stable on the medication(s) for at least 4 weeks prior to Screening Visit 1.
- Symptomatic therapies for AD, including but not limited to donepezil, rivastigmine, galantamine, tacrine, and memantine, are allowed provided that subjects are receiving a stable dose for at least 8 weeks prior to Screening Visit 1 and that they stay on a stable dose while in the study.
- Vaccinations with live or attenuated vaccines are allowed during the study. Administration of any vaccination/booster should not be given <10 days prior to any dosing visit and for 10 days after a dosing visit.

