## 7. STUDY DESIGN

### 7.1. Study Overview

Study 221AD301 is a multicenter, randomized, double-blind, placebo-controlled, parallel-group study in subjects with early AD, including MCI due to AD and a subset of mild AD, followed by an optional 24-month dose-blind LTE study. Approximately 1350 subjects will be enrolled across approximately 150 centers globally. The primary study objective is to evaluate the efficacy of monthly doses of aducanumab on the CDR-SB relative to placebo. Secondary objectives include assessment of the effect of monthly doses of aducanumab on clinical progression as compared to placebo. The safety of monthly doses of aducanumab will also be evaluated.

Subjects will receive infusions of aducanumab or placebo approximately every 4 weeks for approximately 18 months (a total of 20 doses). Subjects will be randomized to receive aducanumab low dose: aducanumab high dose: placebo in a 1:1:1 ratio. The randomization will be stratified by site and ApoE  $\epsilon$ 4 status (carrier or non-carrier). Subject enrollment will be monitored so that approximately 60% to 70% ApoE  $\epsilon$ 4 carriers are enrolled. Enrollment will also be monitored, via interactive response technology (IRT), such that subjects with mild AD represent a small percentage of the total enrolled in the trial.

At the end of the double-blind, placebo-controlled treatment period, subjects who meet the extension entry criteria may enter a 24-month long-term safety and efficacy extension period, with all subjects receiving aducanumab approximately every 4 weeks (a total of 26 doses).

The total duration of study participation for each subject only participating in the placebo-controlled period of the study will be up to approximately 102 weeks, including a series of Screening visits within 8 weeks before administration of the first dose, a 76-week placebo-controlled treatment period, and a safety follow-up (FU) period of approximately 18 weeks after the final dose.

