#### 11.5.1.2. Disallowed Concomitant Therapy

- Medications with platelet anti-aggregant or anti-coagulant properties, except the use of aspirin at a dose of  $\leq 325$  mg per day.
- Non-prescription narcotic medication.
- Immunosuppressive drugs (including systemic corticosteroids). Local corticosteroids (including inhaled and topical corticosteroids) are allowed; certain systemic corticosteroids may be permitted at the Sponsor's discretion.
- Parenteral immunoglobulin, blood products, plasma derivatives, plasma exchange, and plasmapheresis.
- Any investigational drug.

Subjects should be instructed to continue the medications that they were receiving at enrollment (see allowed concomitant therapy above) and avoid starting any new medications or herbal preparations during the study period, as it may confound the results of the study. However, medically indicated medication or treatment should not be withheld. Subjects should inform the Investigator of any changes in medication. The change should be reviewed by the Investigator and the study medical monitor to determine whether the subject's study treatment should be suspended, with the exception of medications used to treat AEs, which would not result in automatic withdrawal. The Sponsor may be consulted if required.

Subjects should have an unscheduled visit for a change in AD medication, and all clinical assessments for the primary and secondary objectives should be performed prior to the change in medication.

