#### 11.5.2. Concomitant Procedures

A concomitant procedure is any therapeutic intervention (e.g., surgery/biopsy, physical therapy) or diagnostic assessment (e.g., blood gas measurement, routine colonoscopy, bacterial cultures) performed between the time the subject is enrolled in the study and until the subject's final clinic visit (including FU visit), unless the subjects is being followed for study-related toxicity.

CONFIDENTIAL

The information contained herein may not be used, disclosed, or published without the written consent of  
Biogen MA Inc.

The use of concomitant therapies or procedures defined above must be recorded on the subject's CRF. AEs related to administration of these therapies or procedures must be documented on the appropriate AE CRF.

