#### **16.2.2.4. Analysis of the Primary Endpoint**

The population for the primary endpoint analysis will be subjects in the ITT population with a baseline and at least one post-baseline CDR-SB score. A mixed model repeated measures (MMRM) model will be used as the primary analysis to analyze change from baseline CDR-SB using fixed effects of treatment, time, treatment-by-time interaction, baseline CDR-SB, baseline CDR-SB by time, baseline MMSE, and baseline ApoE  $\epsilon 4$  status.

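### Baseline use of symptomatic AD drugs is permitted and recorded but is not a term in the v3.0 primary or secondary MMRMs; adding it would give a small gain in precision

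*Protocol*

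**What the plan says.** All references are to Protocol v3.0.

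- **Permitted.** Section 11.5.1.1 says symptomatic AD therapies "are allowed provided that subjects are receiving a stable dose for at least 8 weeks prior to Screening Visit 1", and subjects are to remain on a stable dose during the study. A subject may therefore enter on or off such a drug.
- **Recorded.** Section 11.5.1: "Prior AD medication use within the 12 months prior to Screening will be captured". Section 11.5.2: "The use of concomitant therapies or procedures defined above must be recorded" on the case report form.
- **Randomization.** Section 7.1: "The randomization will be stratified by site and ApoE" ε4 status. Section 9.2 gives the same two factors.
- **Primary model.** Section 16.2.2.4 specifies an MMRM with "fixed effects of treatment, time, treatment-by-time interaction, baseline CDR-SB, baseline CDR-SB by time, baseline MMSE, and baseline ApoE" ε4 status.
- **Secondary models.** Section 16.2.2.5 uses the same form for MMSE, ADAS-Cog 13 and ADCS-ADL-MCI, also without an AD-medication term.
- **Changes during the study.** Section 11.5.1.2 discourages starting new medications, "as it may confound the results of the study", and adds: "Subjects should have an unscheduled visit for a change in AD medication", with the primary and secondary scales done before the change.

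**The concern.** Use of an AD drug at entry may mark subjects whose clinicians saw a need for treatment. In a trial that mixes MCI due to AD with mild AD, it could be associated with how fast CDR-SB worsens over 78 weeks, beyond what baseline CDR-SB and MMSE capture. If so, two small things are lost by leaving it out. The variance it explains stays in the residual, and if the arms happen to differ in use, the estimate is not adjusted for that difference directly.

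The protocol has made a choice here. It defers biomarker selection, the extension analyses and the futility criteria to the SAP, but for the primary and secondary endpoints it writes out the covariates itself. It is therefore fair to ask why a baseline factor that is already collected is absent.

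**Working it through.** **Inputs from Section 16.7:** 450 per arm, difference 0.5, SD 1.92, two-sided alpha 0.05, dropout 30%, power about 90%.

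**Step 1: reproduce the stated power.** Evaluable per arm = 450 × 0.70 = 315. SE of the difference = 1.92 × √(2/315) = 0.153. Power = Φ(0.5/0.153 − 1.96) = 90.5% (90.4% by exact noncentral t). In reverse, 90% power needs 310 evaluable per arm, and 310/0.70 = 443, against 450 planned. The figure reproduces.

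**Step 2: assumptions.** The documents give neither of the next two quantities. Let p be the share on AD drugs at entry, taken as 0.3 to 0.7. Let g be the difference in Week 78 CDR-SB change between users and non-users that remains after the listed covariates, taken as 0.25 to 1.0 points. The top value is generous: it is twice the target difference and half the assumed placebo change of 2.

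**Step 3: formulas.**
- SD of the between-arm difference in use = √(2p(1−p)/315)
- Shift at the 95% limit = 1.96 × that SD × g
- Share of variance explained, R² = p(1−p)g²/1.92²
- Power with the term added: Step 1 with SD 1.92 × √(1−R²)

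At p = 0.5 the SD of the imbalance is √(0.5/315) = 0.0398, so 95% of imbalances lie within ±7.8 percentage points. At p = 0.3 or 0.7 they lie within ±7.2 points.

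| p | g | Shift at 95% limit | Shift in SE | R² | Power with term |
|---|---|---|---|---|---|
| 0.5 | 0.25 | 0.020 | 0.13 | 0.4% | 90.58% |
| 0.5 | 0.5 | 0.039 | 0.26 | 1.7% | 90.93% |
| 0.5 | 1.0 | 0.078 | 0.51 | 6.8% | 92.29% |
| 0.3 or 0.7 | 0.25 | 0.018 | 0.12 | 0.4% | 90.56% |
| 0.3 or 0.7 | 0.5 | 0.036 | 0.23 | 1.4% | 90.85% |
| 0.3 or 0.7 | 1.0 | 0.072 | 0.47 | 5.7% | 92.01% |

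Against the 0.5 target, shifts of 0.020 to 0.078 are 4% to 16%. The power figures take 1.92 as the SD before the term is added. If the existing covariates already reduce it, the starting power is higher.

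**Step 4: type I error without the term.** In 40,000 simulated null trials with 315 per arm and p = 0.5, the unadjusted test rejected in 4.99% (g = 0.5) and 4.98% (g = 1.0). The nominal level holds.

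**The case against.** The strongest reply is that nothing is wrong with the comparison as planned, and most of that reply stands.

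- **Bias.** A reader might infer that imbalance in AD drugs biases the treatment effect or inflates type I error. It does neither. Randomization balances use in expectation, and chance imbalance is part of the sampling variation that the standard error measures; Step 4 bears this out.
- **The protocol's own words.** A reader might infer that the protocol itself calls background AD drugs a confounder. It does not. The sentence in Section 11.5.1.2 is about starting new medications, and the 8-week stability rule and the unscheduled visit are about change. None of these treats stable use at entry as a confounder.
- **Change from baseline.** Baseline scores are taken on a stable dose, so a constant effect on score level is already in the baseline value. Baseline CDR-SB, its interaction with time, and baseline MMSE should absorb part of the severity that prompts prescribing. Only a residual association with rate of decline is left, and its existence is assumed.
- **Choice of covariates.** A short list is legitimate, and other baseline factors could be argued for in the same way. A sensitivity analysis by AD medication may be in the SAP, which is not shown.
- **Superseded text.** A reader might take this as a defect of the current plan. That cannot be shown. The supplied v4.0 breaks off in the schedule tables. It changed the carrier high dose from 6 to 10 mg/kg, so the dose regimens in Section 16 must have been revised; whether the covariates were is unknown.

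What survives is that the factor is already collected, the protocol fixes the model without it, and pre-specifying it costs almost nothing.

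**Conclusion.** This is a minor, optional improvement in precision, not an error that threatens the result. On the assumed ranges, the term would add between 0.1 and 1.8 percentage points of power to about 90.5%. An imbalance at the 95% limit would move the CDR-SB difference by at most about half a standard error, and by about a quarter or less unless the user/non-user difference is well above 0.5 points. Those sizes rest on two quantities that the documents do not give. The conclusion applies to v3.0 and is conditional on v4.0 Section 16 having the same covariates.

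**What to change.** First check the covariate list in v4.0 Section 16. If it is unchanged, add baseline AD symptomatic medication use (yes/no) as a fixed effect in the primary CDR-SB MMRM and in the MMSE, ADAS-Cog 13 and ADCS-ADL-MCI models. Preferably include its interaction with time: a main effect alone forces the same offset at every visit and fits an association with rate of decline poorly.

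Fix this before any unblinding, including the futility look at about 50% of subjects. Added after an imbalance has been seen, it would look post hoc.

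No change to stratification is needed. About 150 sites by two ApoE ε4 strata already give some 300 cells for 1350 subjects, or 4.5 per cell.

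The cost is a few degrees of freedom: one for the main effect and two more for the interaction, given the three clinical assessment visits in Section 7.3. No new data or subjects are required.

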#### 11.5.1.2. Disallowed Concomitant Therapy

- Medications with platelet anti-aggregant or anti-coagulant properties, except the use of aspirin at a dose of  $\leq 325$  mg per day.
- Non-prescription narcotic medication.
- Immunosuppressive drugs (including systemic corticosteroids). Local corticosteroids (including inhaled and topical corticosteroids) are allowed; certain systemic corticosteroids may be permitted at the Sponsor's discretion.
- Parenteral immunoglobulin, blood products, plasma derivatives, plasma exchange, and plasmapheresis.
- Any investigational drug.

Subjects should be instructed to continue the medications that they were receiving at enrollment (see allowed concomitant therapy above) and avoid starting any new medications or herbal preparations during the study period, as it may confound the results of the study. However, medically indicated medication or treatment should not be withheld. Subjects should inform the Investigator of any changes in medication. The change should be reviewed by the Investigator and the study medical monitor to determine whether the subject's study treatment should be suspended, with the exception of medications used to treat AEs, which would not result in automatic withdrawal. The Sponsor may be consulted if required.

Subjects should have an unscheduled visit for a change in AD medication, and all clinical assessments for the primary and secondary objectives should be performed prior to the change in medication.

#### 11.5.2. Concomitant Procedures

A concomitant procedure is any therapeutic intervention (e.g., surgery/biopsy, physical therapy) or diagnostic assessment (e.g., blood gas measurement, routine colonoscopy, bacterial cultures) performed between the time the subject is enrolled in the study and until the subject's final clinic visit (including FU visit), unless the subjects is being followed for study-related toxicity.

CONFIDENTIAL

The information contained herein may not be used, disclosed, or published without the written consent of  
Biogen MA Inc.

The use of concomitant therapies or procedures defined above must be recorded on the subject's CRF. AEs related to administration of these therapies or procedures must be documented on the appropriate AE CRF.

#### **11.6. Continuation of Treatment**

No further provisions are made for access to the study treatment. If aducanumab is proven to be beneficial, all regulatory requirements regarding poststudy access will be met.

CONFIDENTIAL

The information contained herein may not be used, disclosed, or published without the written consent of Biogen MA Inc.

## 12. STUDY TREATMENT MANAGEMENT

Study site staff should follow the DHA for specific instructions on the handling, preparation, administration, and disposal of the study treatment. The DHA supersedes all other references (e.g., protocol).

Study treatment must be dispensed only by a pharmacist or appropriately qualified staff. Study treatment is to be dispensed only to subjects enrolled in this study. Once study treatment is prepared for a subject, it can be administered only to that subject. Study treatment vials are for one-time use only; any study treatment remaining in the vial must not be used for another subject.

### 12.1. Aducanumab

Research Name: BIIB037  
Generic Name: Aducanumab  
Trade Name(s): Not applicable  
Synonyms: Fully human, IgG1, anti-A $\beta$  monoclonal antibody

Aducanumab is a recombinant human antibody expressed in a Chinese hamster ovary cell line [REDACTED], purified to a high degree of purity and formulated as a liquid. Aducanumab is an IgG1 consisting of 2 heavy and 2 kappa light chains connected by inter-chain disulfide bonds. [REDACTED] Aducanumab is purified from the media and formulated as a liquid.

Aducanumab is supplied as a liquid drug product containing aducanumab 50 mg/mL, [REDACTED]

[REDACTED] Aducanumab is manufactured in accordance with Good Manufacturing Practices.

The contents of the label will be in accordance with all applicable regulatory requirements. Aducanumab should not be used after the expiration date.

#### 12.1.1. Aducanumab Preparation

The individual preparing aducanumab should carefully review the instructions provided in the DHA.

Aducanumab is to be administered by IV infusion following dilution into saline.

If the packaging is damaged, or if there is anything unusual about the appearance or attributes of the vials or drug it should not be used. The vial in question should be saved at the study site, and the problem immediately reported to Biogen.

CONFIDENTIAL

The information contained herein may not be used, disclosed, or published without the written consent of Biogen MA Inc.

### **12.1.2. Aducanumab Storage**

Study treatment must be stored in a secure location. Aducanumab is to be stored at 2° to 8°C (36°F to 46°F), in a locked storage container with limited access. Aducanumab should be protected from light, protected from freezing, and should not be shaken. If administration of the prepared aducanumab is delayed for more than 2 hours, then it should be kept at 2° to 8°C until use. If administration of the prepared aducanumab is delayed for more than 24 hours, it must be discarded. For the most up-to-date storage requirements, follow the instructions provided in the DHA.

### **12.1.3. Aducanumab Handling and Disposal**

The Investigator must return all used and unused vials of aducanumab as instructed by Biogen (or its designee), unless approved for onsite destruction.

If any aducanumab supplies are to be destroyed at the study site, the institution or appropriate site personnel must obtain prior approval from Biogen by providing, in writing, the destruction policy or details of the method of destruction. After such destruction, Biogen must be notified in writing of the details of the study treatment destroyed (e.g., lot or kit numbers, quantities), the date of destruction, and proof of destruction.

### **12.1.4. Aducanumab Accountability**

Accountability for study treatment is the responsibility of the Investigator. The study site must maintain accurate records demonstrating dates and amount of study treatment received, to whom dispensed (subject-by-subject accounting), and accounts of any study treatment accidentally or deliberately destroyed.

Unless otherwise notified, all vials both used and unused, must be saved for study treatment accountability. By the end of the study reconciliation must be made between the amount of aducanumab supplied, dispensed, and subsequently destroyed or returned to Biogen. A written explanation must be provided for any discrepancies.

## **12.2. Placebo**

The placebo (0.9% sterile sodium chloride for injection) will be provided by the site in the form of 100 ml saline IV bags.

## **12.3. Additional Protocol-Designated Products**

Refer to the DHA for infusion-related supply specifications.

To confirm amyloid pathology at Screening, PET scans will be performed using Amyvid™ (F-florbetapir), Vizamyli™ (F-flutemetamol), or Neuraceq™ (F-florbetaben). For those subjects participating in the amyloid PET substudy, Screening and FU scans must be performed using Amyvid. For subjects participating in the PET substudy in Japan, Vizamyli (F-flutemetamol) will be used. For details on PET imaging ligands, [REDACTED] refer to the procedural manual for PET.

CONFIDENTIAL

The information contained herein may not be used, disclosed, or published without the written consent of Biogen MA Inc.

### **13. EFFICACY, PHARMACOKINETIC, AND PHARMACODYNAMIC ASSESSMENTS**

Refer to Section 4.2 for the timing of assessments.

#### **13.1. Clinical Efficacy Assessments**

The following clinical assessments will be performed to evaluate the efficacy of aducanumab:

- CDR
- MMSE
- ADAS-Cog 13
- ADCS-ADL-MCI
- NPI-10

It is recommended that clinical assessments be performed at the same time of day for subjects during their study visits.

Some tests will require the informant/care partner to participate and answer questions regarding the subject's daily activities and cognitive capabilities.

The recommended order of administration of the clinical assessments is described in the Study Reference Guide.

#### **13.2. Pharmacokinetic Assessments**

Serum concentrations of aducanumab will be measured using a validated assay.

#### **13.3. Pharmacodynamic Assessments**

The following tests will be performed to assess the pharmacodynamic properties of aducanumab:

- Serial measurement of amyloid plaque burden in certain areas of the brain as measured by amyloid PET (in a subset of approximately 400 subjects participating in the amyloid PET cohort).

Only sites with capabilities of performing F-florbetapir PET will be allowed to perform this assessment. Investigator participation in this part of the study is optional and contingent upon approval by his/her ethics committee (EC) or institutional review board (IRB). If the Investigator is not participating or the test is not approved by his/her EC/IRB, the relevant section of the ICF will not be applicable to that site.

Subject participation in this part of the study is optional at participating sites. Informed consent must be recorded in the CRF. Detailed PET scanning protocols will be described in a separate procedural manual for PET. Approximately 400 subjects are expected to participate in the amyloid PET substudy.

CONFIDENTIAL

The information contained herein may not be used, disclosed, or published without the written consent of Biogen MA Inc.

- [REDACTED]  
[REDACTED] for MRI.
- [REDACTED]  
[REDACTED]
- [REDACTED]  
[REDACTED]
- [REDACTED]  
[REDACTED]
- [REDACTED]  
[REDACTED]

